The aims of this pilot study are to (1) determine the feasibility and acceptability of the M-MILK intervention by nurses and parents, (2) determine the feasibility of recruitment and retention, (3) obtain variability data for sample size estimation, and (4) evaluate the charges and costs of the NICU hospitalization and 2 months CA care between the M-MILK and control groups. M-MILK will be considered feasible if M-MILK is implemented by nurses or parents after every hands-on care and during the beginning of a full gavage feeding at least 90% of the time. The M-MILK acceptability by nurses and parents will be determined via M-MILK Acceptability Questionnaire. Recruitment and retention will be considered feasible if at least 50% of infants approached for participation enrolled, 90% of infants completed all inpatient data collection, and at least 50% of infants completed post-discharge follow-ups.

V. Administrative Organization

Participants will be enrolled in the Neonatal Intensive Care Unit (NICU) at Loyola University Medical Center (LUMC) (Maywood, IL). The inpatient components of the study protocol will be conducted in the NICU at LUMC. The post-discharge follow-up components of the study protocol will be conducted via phone/zoom interview. Data storage and management will be carried out via REDCap (version 10.4.0, Vanderbilt University) and a secured research network drive, hosted by the Loyola University Chicago (Maywood, IL).

Upon sample collection, buccal swab and fecal samples will be labeled only with study ID numbers and collection date, and stored in a locked cabinet in a locked laboratory at Loyola University Chicago (LUC) Center for Translational Research and Education (CTRE). All samples will be stored at room temperature. Quarterly, the buccal swab samples and fecal samples will be securely transported in a biospecimen transfer container (Saf T Pak, Austell, GA) via car to Rush University Medical Center Genomics and Microbiome Core Facility (Rush) (Chicago, IL) for processing and analyses. A Service Agreement between LUC and Rush will be submitted through LUC Research Portal.

VI. Study Design

a. Design

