The M-MILK pilot study ($N = 12$) is a 2-group, 6 per group, parallel design, and longitudinal randomized controlled trial. We will recruit preterm infants who are born between 22 to 33 weeks gestational age. We will compare the outcomes between the M-MILK and attention control groups. Infants will be enrolled into the study as soon as possible after they are admitted to the NICU. If infants are in the M-MILK group, M-MILK will begin on day 3 of life after every hands-on care and during the beginning of a full gavage feeding. We will measure outcomes using validated methodologies at baseline (enrollment), 34 weeks PMA, discharge, and 2 months CA.

b. Setting

The M-MILK pilot study will be conducted in a level III NICU at LUMC (Maywood, IL). The hospital provides care to families with diverse racial, ethnic, and socioeconomic backgrounds. The nursing staff are predominantly registered nurses and advanced nurse practitioners, and the physicians are board certified

neonatologists. Infants are fed using mother's own milk, donor milk, and/or formula. However, we will only include infants who receive mother's own milk or donor's milk.

c. Sample

We will enroll 12 preterm infants (6 per group). Anticipated a 40% attrition rate, we expect the final sample size to be 12 preterm infants. Estimates of average values and variability of continuous measures are acceptable at this sample size using the "rule of 12" as recommended.³¹

VII. Study Procedures

a. Subject Selection Procedures

i. Inclusion/Exclusion Criteria

Inclusion criteria

- Born between 22 to 33 weeks gestational age
- Mother is pumping and infant is receiving mother's own milk and/or donor's milk to be in the intervention group.

Exclusion criteria

- Congenital abnormalities in the digestive, e.g., clef lip and palate, omphalocele
- Necrotizing enterocolitis
- Congenital heart disease that requires surgery

ii. Screening procedures

After infants are admitted to the NICU, we will review their electronic medical records to screen for eligible infants according to the inclusion and exclusion criteria. Once an infant is enrolled into the study, the screening period continues until NICU discharge. The infant will be classified as screen failed and excluded if he/she develops any of the exclusion criteria.

iii. Recruitment Procedures

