Parents of eligible infants will be approached during their post-partum hospitalization or in the NICU at LUMC. A research team member will provide details regarding the study purpose, procedures, and answer questions. Parents will be provided with a study brochure. If parents request additional time to make their decision, we will request a phone number and ask permission to follow-up. If parents agree to have their infant participate, a written informed consent and authorization to use and disclose the PHI will be obtained. Parents will receive a copy of their signed informed consent and authorization to use and disclose the PHI. A copy of the informed consent form will be uploaded to the infant's electronic medical record. The original signed consent will be stored in a locked cabinet at LUC CTRE (Maywood, IL). Infant's participation in the study will end after the phone/Zoom interview at 2 months CA. We will provide a \$50 incentive e-gift card at NICU discharge and a \$50 incentive e-gift card at the completion of the post-discharge follow-up, a total of \$100 e-gift card. Premature infants, by virtue of their age, are unable to give consent or assent, and therefore, will not give assent or participate in the informed consent process.

iv. Randomization Procedures

Randomization is controlled by using two computer-generated lists of random numbers that are corresponded to each group: Group 1 (M-MILK) and Group 2 (attention control), balanced so that 1/2 of the infants are in each group. The lists are retained. The random numbers will be printed in order on small cards stated as Group 1 or Group 2. The cards will be placed in envelopes and placed in order in a box. Prior to approaching parents for recruitment, we will open the first envelope in the box to obtain the group assignment. We will request parents to not disclose their group assignment with other parents in the NICU. The research team

members, staff nurses, and parents cannot be blinded to the treatment condition. The research team members need to know which intervention to provide. Staff nurses provide direct care to infants. The two groups are described in the consent form as required by LUC Institutional Review Board.

v. Study Intervention

1. MMILK Intervention

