Charges and costs of care	Healthcare use and associated charges and costs of the NICU hospitalization and 2 months CA care will be extracted from LUMC's electronic health and billing records. For infants receiving care outside LUMC 2 months CA, we will ask the parents about the extent and types of healthcare received outside LUMC. We will evaluate healthcare use, costs, and charges between the M-MILK and control groups. We will also describe the extent and types of healthcare use 2 months CA for infants receiving care outside LUMC at discharge. In the R01 trial, we will use activity-based costing approach to calculate the time and resources costs of delivering the M-MILK intervention by nurses and parents (which may not be fully reflected in the health system billing records), and query NICU hospitalization and 2 months CA healthcare use, charges, and costs to calculate total benefits and costs of M-MILK Intervention vs. control group.	T3 & T4
M-MILK Acceptability Questionnaire	The M-MILK Acceptability Questionnaire will be completed by parents at discharge. The nurses will complete the M-MILK Acceptability Questionnaire at the end of the entire study.	T3 M-MILK Acceptability Questionnaire

Note. EPIC = electronic medical record; GA = gestational age; PMA = postmenstrual age; CA = corrected age; Ongoing = throughout hospitalization from enrollment to discharge; T0 = baseline; T1 = 34 weeks PMA; T2 = oral feeding initiation; T3 = discharge; T4 = 2 months CA

ii. Procedures

Figure 2. After informed consent is obtained, infants will be randomized into: Group 1 (M-MILK) and Group 2 (attention control). All data collection will be conducted in the same manner and at the planned time points for both groups. For all infants, we will collect infant characteristics, NISS, and family NICU activities daily ongoing from EPIC and self-report. All parents will receive an automatic daily text in the morning with a link to report their daily activities with infants when they come to the NICU. All parents are signing up for daily texts for up to 20 weeks to complete daily activities report every day during their participation. All parents will also receive a weekly phone call from a research nurse from enrollment until discharge. M-MILK is primarily implemented by nurses or parents. **At baseline (T0)**, we will conduct the EPDS assessment, and collect parent characteristics,

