Strict confidentiality of data files will be maintained. Data management will be facilitated using REDCap. SAS (v 9.4) will be used for all statistical procedures and analyses. Levels of missingness, variable distributions, and outliers will be examined throughout data collection for quality assurance as well as prior to statistical modeling. We will calculate descriptive statistics for all variables of interest to describe the variability of study variables, and conduct sample size estimation for the planned R01 application. Comparisons will be made using an intent-to-treat approach with participants analyzed in the groups to which they were randomized. Feasibility will be assessed with respect to enrollment, adherence, acceptability, and safety. We will calculate the percentage of infants who (1) were eligible, approached, consented, enrolled, and randomized over the recruitment period, (2) were retained for the duration of the study, (3) completed all inpatient data collection, and (4) completed post-discharge follow-ups. To determine the adherence of M-MILK, we will calculate the daily numbers of completed M-MILK and the daily numbers of expected M-MILK implementation (numbers of hands-on care episodes before full gavage feedings) to obtain the daily percentage of M-MILK completion. We will summarize findings from M-MILK Acceptability Questionnaire by nurses and parents. We will also summarize findings from M-MILK EPIC charting regarding infant's responses and any adverse events to monitor for the safety of M-MILK.

X. Study Timeline

Table 2. The proposed pilot study will require 1 year to complete. During the first 3 months, we will hire and train the team members. We anticipate enrolling 2 infants per month for 9 months. An additional 3 months will be required to complete the intervention and collect study data. Data entry and analyses will be ongoing. We will spend 6 months to complete data analyses. An additional 6 months will be needed to prepare the final report and disseminations.

Table 2. Study Timeline

Activity/Month	Month 1-3	Month 3-12	Month 12-15	Month 15-21	Month 21-27
Preparation & Staff Training	X				
Recruitment & Enrollment		X			
Data Collection		X	X		
Data Entry & Analyses		X	X	X	
Final Reports & Dissemination				X	X

XIII. Literature Cited

1. Barfield WD. Public Health Implications of Very Preterm Birth. *Clin Perinatol*. Sep 2018;45(3):565-577.

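### The randomization section opens the allocation envelope before parents are approached, which removes concealment and contradicts the procedures section, where randomization follows consent

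*Combined protocol and SAP*

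**What the plan says.** Three places in the combined protocol and SAP bear on when the arm becomes known.

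- Section VII.a.iv, Randomization Procedures: "Prior to approaching parents for recruitment, we will open the first envelope in the box to obtain the group assignment". Cards sit in ordered envelopes in a box. The section does not describe the envelopes as sealed or opaque and names no holder outside the recruiting team. The allocation is "balanced so that 1/2 of the infants are in each group". It adds that research team "members, staff nurses, and parents cannot be blinded to the treatment condition".
- Section VII.a.vi, subsection ii, Procedures (text to Figure 2): "After informed consent is obtained, infants will be randomized into: Group 1 (M-MILK) and Group 2 (attention control").
- Section IX, Data Management and Analysis Plan, will report the percentages of infants who "were eligible, approached, consented, enrolled, and randomized over the recruitment period".

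Three further statements matter for the consequences.

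- Section VII.a.i, Inclusion Criteria: "Mother is pumping and infant is receiving mother's own milk and/or donor's milk to be in the intervention group". The Setting text in VI.b restricts all infants to mother's own or donor milk, but does not repeat the pumping condition for controls.
- Section VII.a.iii, Recruitment Procedures: "If parents request additional time to make their decision, we will request a phone number and ask permission to follow-up". What happens to an opened envelope in the meantime, or after a refusal, is not stated.
- Section IV, Study Aims, sets the recruitment criterion: "at least 50% of infants approached for participation enrolled".

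**The concern.** If the envelope is opened first, the people who recruit know the next assignment while they still control who enters the trial. They can pass over or delay an infant, or present the study differently, according to the card they hold. The inclusion criterion worded for the intervention group adds a route: read literally, an infant could be passed over under an M-MILK card and accepted under a control card.

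The plan does compare the groups: on outcomes (VI.a), on charges and costs (Aim 4), and on the microbiome with Mann-Whitney, PERMANOVA and DESeq2 tests (Table 1). Selection before enrolment would enter all of these. The blinded Research Nurse in the fidelity section (VII.a.v) gives no protection, because selection happens before any outcome is assessed.

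The Aim 2 enrolment rate would also come from families approached by a recruiter who knows the arm. In addition, the percentage randomized and the intent-to-treat set become ambiguous, since an infant whose parents decline may already hold an assignment.

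**Working it through.** **Order of steps**

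| Place | Order |
|---|---|
| VII.a.iv Randomization Procedures | open envelope, then approach parents |
| VII.a.vi, ii. Procedures | consent, then randomize |
| IX Analysis Plan (reporting list) | eligible, approached, consented, enrolled, randomized |

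The first two exclude each other. The third is a list of percentages rather than a procedure, so it supports the second only weakly. The plan gives no figure that depends on this point, so there is nothing to reproduce. The calculations below show size under stated assumptions.

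**Steering.** Inputs: n = 6 per group (VI.c; the abstract gives 10) and the 22 to 33 week entry range (VII.a.i). Let d be the difference in gestational age, in weeks, between the two infants involved.

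- Pass-over: one infant is replaced by another under the same card. One arm mean changes, so the shift in the mean difference is d/n.
- Exchange: an infant passed over under one card is enrolled later under the other, and another infant takes the first place. Both arm means change, so the shift is 2d/n.

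| d (weeks) | Pass-over, d/6 | Exchange, 2d/6 | Exchange, 2d/10 |
|---|---|---|---|
| 4 | 0.67 | 1.33 | 0.8 |
| 8 | 1.33 | 2.67 | 1.6 |
| 11 (full range) | 1.83 | 3.67 | 2.2 |

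For comparison with chance: if gestational age were uniform over the 11-week range (an assumption), its SD would be 11/√12 ≈ 3.2 weeks. The standard error of the mean difference would be 3.2 × √(2/6) ≈ 1.8 weeks.

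**Group balance if refused envelopes are used up.** Assumptions: a balanced list of 2h envelopes, all opened; 12 consents; refusal unrelated to arm. Then P(6:6) = C(h,6)² / C(2h,12).

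| Envelopes opened | Uptake | P(6:6) | P(8:4 or worse) |
|---|---|---|---|
| 16 | 75% | 28²/1820 = 0.43 | 0.08 |
| 20 | 60% | 210²/125970 = 0.35 | 0.17 |
| 24 | 50% | 924²/2704156 = 0.32 | 0.22 |

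With independent 1:1 draws, the binomial chance of 6:6 is 924/4096 = 0.23. If an opened envelope is instead kept for the next family, 6:6 is preserved, but that family's arm is known in advance. A balanced 12-envelope list opened only for the 12 consented infants gives 6:6 with certainty.

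**Consent that depends on the arm.** The documents do not say whether parents learn their arm before signing, so this is only a possibility. With 12 approached per arm and assumed uptake of 60% against 40%, the expected split is 7.2 to 4.8. With 70% against 30% it is 8.4 to 3.6. Pooled uptake is 12/24 = 50% in both cases, so the Aim 2 criterion would be met and would not reveal the difference.

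**The case against.** The strongest reply is that this is a pilot. Aims 1 to 3 concern feasibility, acceptability and variability, no efficacy decision depends on the comparison, and the procedures section already states the sound order. If staff follow that section, the fault is one of wording. This tempers the severity but does not remove the point: the dedicated randomization section gives the opposite instruction, and Aim 4 and the microbiome tests do compare arms.

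Several objections to the size stand in part.

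- A simple pass-over, the most direct route, gives half the shift of an exchange. An exchange requires holding an infant for a later card, which is harder when enrolment is meant to follow admission quickly and M-MILK starts on day 3. The 11-week case is a boundary.
- A shift of 0.67 or 1.33 weeks is smaller than the chance standard error of about 1.8 weeks. Systematic selection, however, is not averaged away or covered by the usual error estimates.
- The balance figures depend on envelopes being used up and on assumed list lengths. The balance sentence refers to infants, so reuse is an equally fair reading.
- The uptake rates by arm have no source in the documents.
- Parents of eligible infants are approached after record screening, so eligibility may be settled before the envelope is opened. The documents do not say so.

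That staff and parents cannot be blinded to treatment is accepted, but it does not justify knowing the arm before consent. Concealment up to enrolment is possible in an open-label trial.

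**Conclusion.** The concern holds. The two sections contradict each other, and the randomization section is wrong as written because it discloses the arm to an unblinded recruiting team before parents are approached. For an infant pair 4 to 8 weeks apart, one pass-over shifts the between-group difference in mean gestational age by 0.67 to 1.33 weeks, and one exchange by 1.33 to 2.67 weeks, at 6 per group. Loss of 6:6 balance follows only if refused envelopes are used up. Arm-dependent consent is a risk only.

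The frequency and direction of any steering are unknown, so no bias can be estimated. The point should be corrected before enrolment, because lost concealment cannot be repaired in the analysis, least of all with 12 infants.

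**What to change.** Replace the sentence in VII.a.iv with wording such as:

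> After written informed consent is obtained and eligibility is confirmed, the next sequentially numbered, sealed, opaque envelope is opened to obtain the group assignment. Only consented infants use an envelope.

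Then:

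1. Use one order throughout: screen, approach, written consent, confirm eligibility, open the envelope. The procedures text and the reporting list in section IX already fit it.
2. Reword the milk criterion in VII.a.i so that it is applied identically whatever the arm, reconcile it with the Setting text in VI.b, and confirm it before the envelope is opened.
3. Preferably have someone outside recruitment hold the envelopes, or release assignments through a module in REDCap, which the trial already uses.

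The cost is a short amendment and a change in recruitment workflow. The core change needs no added staff, procedures or infants. One limit remains: with a fixed 6:6 list and an unblinded team, the last assignments can still be deduced.

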The M-MILK group will have access to the educational materials regarding preterm infant care such as Your Guide to Neonatal Intensive Care Unit, Breastfeeding in the NICU, and M-MILK Toolkit video. We will provide parents with two scent hearts to wear and bring back to place near the infant's face. Parents will perform routine care such as taking temperature, bathing, changing diapers, reading, feeding, holding hands, as well as M-MILK when appropriate. Parents will receive an automatic daily text in the morning with a link to report their daily activities with infants when they visit the NICU.

The M-MILK Intervention Protocol is a modified and improved version of previous protocols. This M-MILK protocol is carefully designed by a team of neonatal experts, with a strong focus on developmentally appropriate, trauma informed care, and family friendly language. M-MILK is implemented at day 3 of life even if the infant requires respiratory support and/or mechanical ventilation. M-MILK is implemented after every hands-on care and during the beginning of a full gavage feeding. Infants receive M-MILK as droplets via a 1-ml syringe. In our NICU, oral feeding attempts are initiated at approximately 33 to 34 weeks PMA and based on the infant's pre-feeding cues. M-MILK is not offered with oral feeding attempts since the feeding itself is considered a positive experience. We will use either mother's own milk and or donor's milk depending on availability. Infants may receive up to 1 mL of milk each time based on their cues and responses. The 1 mL volume intake is included as part of their oral caloric intake. M-MILK is provided by the infant's nurse or parents. Parents are encouraged and supported to provide M-MILK when appropriate with the nurse's supervision.

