Postpartum Bonding Questionnaire	Parent-infant bonding will be evaluated by the Postpartum Bonding Questionnaire (PBQ). The PBQ comprises four subscales, i.e., general bonding disorders (12 items; 1, 2, 6, 7, 8, 9, 10, 12, 13, 15, 16, 17), severe mother-infant relationship disorders (7 items; 3, 4, 5, 11, 14, 21, 23), infant-focused anxiety (4 items; 19, 20, 22, 25), and risk of abuse (2 items; 18, 24). The total cumulative score, ranging from 0 to 125, is also used to screen for general bonding disorders (cut-off score ≥ 26), and severe bonding disturbances (cut-off score ≥ 40). The items are scored on a 6-point Likert scale (0-Always to 5-Never). Parents scoring ≥ 26 , (indicating risk of general bonding disorders) or ≥ 40 (indicating risk of severe bonding disturbances) should seek medical attention. Parents scoring "rarely", "sometimes", "quite often", "very often", or "always" for item 18 "I have done harmful things to my baby" or item 24 "I feel like hurting my baby" indicates risk of child abuse. In this case, it is our responsibility to report it to the state's child protective agency. If the infant is in immediate danger, the research staff will be instructed to inform the parents of their immediate concerns for the infant's safety, report the incident using a cellular phone, and call 911 until appropriate officials arrive. The PI will be informed of the family's condition and always be available by phone or in person for consultation and instruction. As part of the training of our research team, the team will review content related to reporting of child neglect and abuse.	T1, T3, T4 PBQ & Self-report
Pumping and breastfeeding	Mothers will report the following: pumping initiation date, pumping cessation date, pumping at discharge (yes/no), pumping at 2 months CA (yes/no), breastfeeding initiation date, breastfeeding cessation date, breastfeeding at discharge (yes/no), & breastfeeding at 2 months CA (yes/no).	Ongoing Self-report

Family daily NICU activities	Parents will report the following: (1) How many hours were you able to visit your baby today? (2) What activities did you do with your baby while you were visiting? The answer choices for question (2) for parents in the M-MILK group are: M-MILK, skin-to-skin, feeding, taking temperature, bathing, changing diaper, reading, holding hands.	Ongoing Self-report

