Infant characteristics	race/ethnicity, & sex, GA at birth, birthweight, 5-minute Apgar score, small for gestational age (yes/no), intra-uterine growth restriction (yes/no), PROM (yes/no), medical diagnoses & therapies, daily weight gain, PMA at discharge, duration of time from initiation of oral feeding to discharge, & duration of NICU hospitalization; daily oral feeding intake, daily type of milk (mother's own milk, donor's milk, or formula), duration of tube feeding, duration of time from initiation of oral feeding to full oral feeding, & PMA at initiation & full oral feeding.	Ongoing EPIC
Infant medical severity	Infant medical severity will be measured via the Neonatal Medical Index Classification (NMI), range 1-5, 1 as absence of serious medical problems & 5 as the most serious complications. ³⁷	T3 EPIC
Early life stress	Early life stress will be measured daily by the modified Neonatal Infant Stressor Scale (NISS) ³⁸ using data from the EPIC during the entire NICU hospitalization. The Neonatal Infant Stressor Scale (NISS): ³⁸ summary scores, 47 acute interventions & 23 chronic conditions, weighted from 2-5, 2 as 'a little stressful' & 5 as 'extremely stressful'. ³⁹ Predictive & construct validity were established, i.e., correlations between higher stress scores & brain structural changes, ⁴⁰ & poorer neurobehaviors. ^{38,41}	Ongoing EPIC

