buccal swab and fecal samples. For infants in the M-MILK group, the clinical team will place an order in EPIC for M-MILK to be provided starting on day 3 of life according to the M-MILK protocol. We will also schedule an in-person 30-minute M-MILK training session with parents in the M-MILK group, within 1 week of enrollment, provided by a research nurse. Parents in the M-MILK group are encouraged and supported to provide M-MILK when appropriate with the nurse's supervision. **At 34 weeks PMA (T1)**, we will collect PBQ, buccal swab and fecal samples. **At oral feeding initiation (T2)**, we will collect the EFS, and NCAST-Feeding video recording. Day of initiation of oral feeding is defined as the first of at least two consecutive days when the infant is able to orally consume $\geq 10\%$ of their prescribed feedings. Infants will be fed by nurses, speech therapist, or PI. We will implement the same feeding protocol, e.g., side-lying and swaddling during feeding. **During the week of planned discharge (T3)**, we will conduct EPDS, PSS: NICU, PDR, PBQ, Pumping and Breastfeeding, NMI, NAPI, and EFS assessments. We will collect NCAST-Feeding video recording, buccal swab and fecal samples. For the NCAST-Feeding video recording, both parents and infants will be recorded. Parents will also complete the M-MILK Acceptability Questionnaire at T3. For EFS and NAPI assessments, we will video record the assessments, when possible, to obtain videos for inter-rater reliability. **At 2 months CA (T4)**, we will send parents the fecal and buccal sample collection kits via USPS mail service. We will also conduct a phone/Zoom interview to complete the EPDS, PBQ, ASQ-3, and NeoEAT assessments. During the phone/Zoom interview, we will also provide parents instructions on how to collect buccal and fecal samples and securely send them back to us.

VIII. Safety Monitoring Plan

a. Potential Risk

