IRB oversight and approval will be based on 45CFR 46 HHS criteria. We anticipate our study will be determined to be no more than "minimal risk". The M-MILK intervention's safety has been demonstrated in infants as young as 22 weeks GA. According to the M-MILK protocol, nurses or parents will carefully observe infants' cues and responses during the M-MILK intervention and stop the administration if infants do not engage or exhibit any signs of distress. Thus, there is minimal risk associated with this protocol. Every effort will be made to minimize the risks. There may be risks associated with administration of M-MILK and collecting buccal swab samples including gagging and minor discomfort. Of note, these risks are no more expected risks to infants than what they might experience during a typical day, routine oral care, or feeding. Nurses will document infants' responses or any unexpected and serious adverse events to M-MILK intervention in the M-MILK Documentation paper sheet. A research nurse will review the documentation and report to PI if there are any unexpected and serious adverse events. For the NAPI assessment, we will perform maneuvers such as partially removing swaddle blanket, gentle stretching/bending of arms and legs, gently picking up, and stimulating vision and hearing with soft rattle sounds and talking voices. These maneuvers may pose minimal risks such as feeling cold, and mild discomfort due to stretching/bending/picking up, or noises. Of note, these risks are no more expected risks to infants than what they might experience during a typical day, routine care, or physical exam. Additionally, this research also carries a minimal risk of loss of data confidentiality/security. We also recognize that there are unique risks related to loss of confidentiality regarding a participant's epigenetic and microbiome data; however, we consider this risk to be rare.

b. Adequacy of Protection Against Risks

i. Informed Consent and Assent

The potential risks will be presented to the parents prior to enrollment. If parents are interested in having their preterm infants participate in the study, written informed consent will be obtained. Alternatively, the potential preterm infant will receive standard care if the parents choose to not enroll in the study. Premature infants, by virtue of their age cannot give consent or assent and therefore will not give assent or participate in the informed consent process.

ii. Protections Against Risk

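### Could M-MILK droplets count toward the 10% rule that dates oral-feeding initiation, and so lower the bar in one arm?

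*Combined protocol and SAP*

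**What the plan says.** Under MMILK Intervention (section VII.a.v.1), infants in the M-MILK arm may take up to 1 mL by mouth each time, guided by their cues, at the start of full gavage feeds from day 3 of life. The section adds that "The 1 mL volume intake is included as part of their oral caloric intake". It also states that "M-MILK is not offered with oral feeding attempts since the feeding itself is considered a positive experience", and places the first oral attempts at about 33 to 34 weeks PMA.

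The Procedures text defines the day of initiation (T2) as "the first of at least two consecutive days when the infant is able to orally consume" at least 10% of prescribed feedings, and continues: "Infants will be fed by nurses, speech therapist, or PI". EFS and the NCAST-Feeding video are collected at T2.

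Table 1, Infant characteristics, takes "daily oral feeding intake, daily type of milk" from EPIC, along with "duration of time from initiation of oral feeding to full oral feeding, & PMA at initiation & full oral feeding" and the time from initiation to discharge.

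On recording, section VIII.a has nurses document infants' responses "in the M-MILK Documentation paper sheet", while section IX refers to EPIC charting of M-MILK responses and to daily counts of completed administrations. No section says where the droplet volume is recorded.

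**The concern.** The T2 definition gives a percentage without a unit and does not mention M-MILK, while another section calls the droplet volume oral intake. Controls receive no droplets, so any pooling would differ by arm. If a data manager computed the 10% by volume from a charted total that included droplets, an M-MILK infant could reach T2 with less real feeding than a control infant.

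The consequences would pull in opposite directions. PMA at initiation would look lower, which flatters M-MILK. The times from initiation to full oral feeding and to discharge would look longer, which counts against it. The first EFS and NCAST-Feeding would be done slightly earlier in one arm, and charted daily oral intake would be slightly higher. Time to full oral feeding is one of the benefits the Background cites for earlier versions of this kind of intervention, so readers would notice it.

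**Working it through.** **Which reading does the text support?**

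- M-MILK belongs to full gavage feeds and is withheld at oral attempts. It starts on day 3; oral attempts start at about 33 to 34 weeks PMA. The protocol treats these as different events.
- The parent activity report lists the two separately: "M-MILK, skin-to-skin, feeding, taking temperature, bathing, changing diaper, reading, holding hands".
- Section IX counts M-MILK administrations as their own daily series for adherence.
- T2 triggers an observed, rated feeding. The people named as feeding are nurses, a speech therapist or the PI, whereas M-MILK is given by nurses or parents. Nurses appear in both lists, so this point is only mild support.
- The pooled reading leads to an odd result. At 1 mL with every feed of V mL, the droplet share is 1/V, which reaches 10% whenever V is 10 mL or less. An infant on small gavage feeds would then have initiated oral feeding with no oral attempt at all. The definition is unlikely to mean that.

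The caloric sentence reads as nutritional accounting. Nothing links it to the T2 percentage.

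**How large would the effect be if droplets were pooled by volume?**

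The plan states no figure to reproduce. Let f be the share of feeds with M-MILK, m the mL per administration and V the prescribed mL per feed. The bar falls by

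points = 100 × f × m / V.

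From the documents: m is at most 1 mL, and the adherence criterion is 90%. Assumed: 8 feeds a day, V, the number of oral feeds, and a mean of 0.5 mL as the lower dose.

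| Case | V = 30 mL | V = 40 mL | V = 50 mL |
|---|---|---|---|
| 1 of 8 feeds oral (f = 7/8), m = 1 | 2.9 | 2.2 | 1.75 |
| same, 90% adherence | 2.6 | 2.0 | 1.6 |
| 2 of 8 feeds oral (f = 6/8), m = 1 | 2.5 | 1.9 | 1.5 |
| f = 7/8, m = 0.5 | 1.5 | 1.1 | 0.9 |
| f = 6/8, m = 0.5 | 1.25 | 0.9 | 0.75 |

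The first cell is 100 × 7/240 = 2.9. The lowest is 100 × 0.75 × 0.5/50 = 0.75. An upper extreme takes an assumed 1.5 kg infant at 120 mL/kg/day, so 180 mL a day, with 1 mL at all 8 feeds: 100 × 8/180 = 4.4. The range is therefore about 0.75 to 4.4 points. A figure of 2 to 3 points needs close to the maximum dose at nearly every feed.

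**What would that do to the T2 date?**

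If real oral intake rises r points a day, the shift is points / r. For 2.2 to 2.9 points:

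- r = 1: 2.2 to 2.9 days
- r = 2: 1.1 to 1.5 days
- r = 5: 0.4 to 0.6 days

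Halve these at 0.5 mL. The documents give no r, and intake need not rise smoothly. With 8 feeds, one complete oral feed is 1/8 = 12.5% of volume and passes unaided. With one oral feed of 30 mL, the bar is 24 of 240 mL, or 24/30 = 80% of that feed. With 7 mL of droplets it is 17/30 = 57%. Droplets change the classification only when the infant takes between about 57% and 80% of that feed.

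If the 10% is by number of feeds, droplet volume has essentially no effect on T2.

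**The case for a change.** The best argument for a change is that the wording does not exclude pooling, the distortion would differ by arm, and clarification would cost a sentence or two. Withholding M-MILK at oral attempts governs when it is given, not what enters a daily total, and droplets continue at the remaining gavage feeds on the days when T2 is decided. Staff nurses and research team members know the allocation, which is a reason not to leave a rule to judgment. T2 also sets the time of the first EFS and NCAST-Feeding, and the pilot data will inform the planning of the next trial.

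The textual part stands: the unit is missing and M-MILK is not mentioned. The missing unit alone, however, applies equally to both arms and creates no bias. Bias needs four things together: a volume count, droplet volume actually charted, that volume pooled with oral feeding intake, and T2 read from the pooled total. The documents establish none of these and describe recording responses and counts, not volumes. No effect on the SDs used for planning has been shown. Subtracting droplet volume would itself need a record of that volume; if only counts exist, completions × 1 mL gives an upper bound.

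**Conclusion.** No change to the plan follows. This is a gap in a written definition that an analyst would fill sensibly: in context, initiation of oral feeding means feeding, and droplets given at the start of a gavage feed would be left out.

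If they were pooled by volume, the bar would drop by about 0.75 to 4.4 points, with T2 moving by anything from a fraction of a day to about three days in the cases worked above. Those figures rest on assumed feed volumes, oral feeds per day, droplet doses and rates of progress that the documents do not give; under a count of feeds the effect essentially vanishes.

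The exposed items are PMA at initiation, durations measured from initiation, daily oral intake (up to 7 mL on such days) and the timing of the T2 EFS and NCAST-Feeding. Section IX plans descriptive statistics and names no test for the T2-anchored variables, and Study Design gives 6 infants per group. The recruitment, retention and adherence criteria do not use T2. PMA at full oral feeding and the T3 and T4 measures are essentially unaffected.
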